- f. Height measurement performed at screening only. If height cannot be measured at the screening visit, it can be collected at any time during the course of the study, but should be recorded for the screening visit. Weight measurement performed at screening and day 1 of each cycle.
- g. The following vital sign assessments schedules apply:
 - At C1D1 and any visit when pembrolizumab and ASP0739 are administered together, vital signs are obtained predose (-1 hour from start of pembrolizumab infusion), within 15 min prior to start of the pembrolizumab infusion, 15 min (-5 to +10 min window) after the start of pembrolizumab infusion, at the end of pembrolizumab infusion (-5 to +10 min window), 30 min (\pm 10 min) after completion of the pembrolizumab infusion, within 15 min prior to start of ASP0739 infusion, every 15 min (-5 to +10 min window) during ASP0739 infusion, at the end of ASP0739 infusion (-5 to +10 min window), and post dose (+30 min, +1, +2, +3 and +4 hours [\pm 10 min window each] from end of ASP0739 infusion).
 - ASP0739 dosing only: vital signs will be obtained within 15 min prior to start of ASP0739 infusion, every 15 min (-5 to +10 min window) during ASP0739 infusion, at the end of ASP0739 infusion (-5 to +10 min window), as well as, 30 min (\pm 5 min), 1 hour (\pm 10 min) and 2 hours (\pm 10 min) after completion of the ASP0739 infusion. If participants are still available, additional optional vital sign assessments 3 hours (\pm 10 min) and 4 hours (\pm 10 min) after completion of the ASP0739 infusion will be obtained.
 - Pembrolizumab dosing only: vital signs will be obtained within 15 min prior to start of the pembrolizumab infusion, -15 min (-5 to +10 min window) after the start of pembrolizumab infusion; at the end of pembrolizumab infusion (-5 to +10 min window) and at 30 min (\pm 10 min) after completion of the pembrolizumab infusion for participants in the combination therapy.
- h. Obtain predose.
- i. If performed within 2 weeks of screening (prior to ICF and performed as part of standard of care), then do not need to be repeated. If participants present positive troponin levels or new onset of cardiovascular symptoms, MUGA or ECHO should be performed.

Footnotes continued on next page

- j. 12-lead ECGs will be recorded in triplicate (at least 2 min apart per time point) and transmitted electronically for central reading. On IP administration days, ECG will be obtained:

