- a. Cycles 1 through 6 represent ASP0739 single agent or combination of ASP0739 and pembrolizumab therapy; each cycle is 28 days.
- b. After the first 2 cycles, participants who have not met any individual treatment discontinuation criteria and are receiving clinical benefit (defined as radiological response or SD, or reduction of disease-related symptoms) will continue further treatment of ASP0739 as decided by the investigator.
- c. After the first 4 cycles, participants who achieve PR or SD may continue further treatment of ASP0739 in cycles 5 and 6. Participants who reach CR will not receive additional doses of ASP0739.
- d. Participants in combination therapy only will continue to receive pembrolizumab as monotherapy for doses 5 up to 17. If participant receives at least 1 dose of ASP0739 but discontinues combination treatment of ASP0739 at any time prior to C5D15, then the participant may continue pembrolizumab as monotherapy for up to 96 weeks for a total of 17 doses of pembrolizumab total for the study.
- e. Height measurement performed at screening only. If height cannot be measured at the screening visit, it can be collected at any time during the course of the study, but should be recorded for the screening visit. Weight measurement performed at screening and day 1 of each cycle.
- f. The following vital sign assessments schedules apply:
 - At C1D1 and any visit when pembrolizumab and ASP0739 are administered together, vital signs are obtained predose (-1 hour from start of pembrolizumab infusion), within 15 min prior to start of the pembrolizumab infusion, 15 min (-5 to +10 min window) after the start of pembrolizumab infusion, at the end of pembrolizumab infusion (-5 to +10 min window), 30 min (\pm 10 min) after completion of the pembrolizumab infusion, within 15 min prior to start of ASP0739 infusion, every 15 min (-5 to +10 min window) during ASP0739 infusion, at the end of ASP0739 infusion (-5 to +10 min window), and post dose (+30 min, +1, +2, +3 and +4 hours [\pm 10 min window each] from end of ASP0739 infusion).

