 - ASP0739 dosing only: vital signs will be obtained within 15 min prior to start of ASP0739 infusion, every 15 min (-5 to +10 min window) during ASP0739 infusion, at the end of ASP0739 infusion (-5 to +10 min window), as well as, 30 min (\pm 5 min), 1 hour (\pm 10 min) and 2 hours (\pm 10 min) after completion of the ASP0739 infusion. If participants are still available, additional optional vital sign assessments 3 hours (\pm 10 min) and 4 hours (\pm 10 min) after completion of the ASP0739 infusion will be obtained.
 - Pembrolizumab dosing only: vital signs will be obtained within 15 min prior to start of the pembrolizumab infusion, -15 min (-5 to +10 min window) after the start of pembrolizumab infusion; at the end of pembrolizumab infusion (-5 to +10 min window) and at 30 min (\pm 10 min) after completion of the pembrolizumab infusion for participants in the combination therapy.
- g. Obtain predose.
- h. Obtain predose if participant receives pembrolizumab at the same visit.
- i. If performed within 2 weeks of screening (prior to ICF and performed as part of standard of care), then do not need to be repeated. If participants present positive troponin levels or new onset of cardiovascular symptoms, MUGA or ECHO should be performed.
- j. 12-lead ECGs will be recorded in triplicate (at least 2 min apart per time point) and read locally. On IP administration days, ECG will be obtained:

Footnotes continued on next page

- At C1D1 and any visit when pembrolizumab and ASP0739 are administered together: ECGs are obtained predose (-1 h from start of pembrolizumab infusion) and 1 to 2 h post dose of ASP0739.
- ASP0739 dosing only: ECGs are obtained predose (-1 h from start of ASP0739 infusion) and 1 to 2 h post dose of ASP0739.
- Pembrolizumab dosing only: ECGs are obtained predose (-1 h from start of pembrolizumab infusion) and 1 to 2 h post dose of pembrolizumab.

k. Includes medications taken within 28 days prior to C1D1. Include all anticancer treatment received 28 days prior to IP administration.

l. Urine or serum pregnancy test will be performed in women of childbearing potential. On treatment visit days, test must occur prior to IP administration.

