6.1.1 Investigational Product Administration

ASP0739 will be diluted with Lactated Ringer's injection to approximately 50 mL and administered by intravenous infusion at 4 to 6 mL/min infusion rate through a dedicated intravenous line every 28 days during treatment beginning on C1D1.

Pembrolizumab will be administered at a dose of 400 mg via 30-min intravenous infusion every 6 weeks beginning on C1D1. Sites should make every effort to target infusion timing to be as close to 30 min as possible. However, given the variability of infusion pumps from site to site, a window between -5 min and +10 min is permitted (i.e., infusion time is 30 min (-5 min/+10 min)). The pembrolizumab infusion should be completed at least 1 hour prior to the ASP0739 injection for participants in the ASP0739 and pembrolizumab combination therapy arms.

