- Site has been restricted to treating patients with conditions outside of the scope of the study
- Site personnel have temporarily relocated the conduct of the study to a location that place a burden on the participant with respect to time and travel
- Participant(s) have temporarily relocated from the current study site to an alternate study site avoid placing a burden on the participant with respect to travel

- Participant(s) have temporarily relocated from their home location and the new distances from the site would cause undue burden with respect to time and travel
- Participant has risk factors for which traveling to the site poses an additional risk to the participant's health and safety

Adherence to the original protocol as reflected in the schedule of assessment [Table 1](#) to [Table 4](#) is expected, where plausible, in the case of a crisis. The alternate measures as noted in [Table 18](#) below are only permissible in the event of a crisis, and after discussing the need with the Astellas medical monitor to implement the alternate measures. This is to allow for continuity of receiving IP and maintaining critical safety and efficacy assessments for patients participating in the study at a time of crisis.

If one or more of the alternate measures noted below is implemented for a participant, the site should document in the participant's source document the justification for implementing the alternate measure and the actual alternate measures that were implemented, along with the corresponding time point(s).

Alternative Schedule of Assessments in Response to a Crisis

No alternative measures are permissible for C1D1 and ASP0739 and/or pembrolizumab dosing days during combination therapy.

Table 18 Study Interruption: Schedule of Assessments – Dose Escalation Cohort and Safety Lead-in Combination Cohort

	Alternate Approach(es)	Treatment ^a																		Pembrolizumab Mono-therapy	EOT ^{e,w}		
		Cycle 1						Cycle 2						Cycles 3 to 4 ^b				Cycles 5 to 6 ^c				Doses 5 to 17 ^d	
Visit Days		1	2	4	8	15	22	1	2	4	8	15	22	1	8	15	22	1	8	15	22 ^w	Every 6 weeks	
Window (days)		0	± 1	± 1	± 1	± 1	± 1	0	± 1	± 1	± 1	± 1	± 1	± 3	± 1	± 1	± 1	± 3	± 1	± 1	± 1	± 3	+ 7
Physical Examination ^f	Except for ASP0739 and/or Pembrolizumab administration days at study site, may be obtained at local facility and results submitted to PI	X ^f	X		X	X	X	X ^f	X		X	X	X	X ^f	X	X	X	X ^f	X	X	X ^f	X ^f	

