- s. In the combination therapy arm, pembrolizumab will be administered as an intravenous infusion over 30 min followed by ASP0739 administration at least 1 hour after pembrolizumab administration. For participants enrolled in Japanese safety lead-in, C1D8 assessments should be performed prior to discharge from hospital.
- t. Samples collected at pembrolizumab doses 5, 7, 9, 11 and 13 only.
- u. Samples collected at pembrolizumab doses 5 and 7 only.
- v. Sample collected at the time of discontinuation due to disease progression.
- w. If participant is completing all assessments within cycle 6, EOT assessment will be on C6D22 (± 3 days) or prior to the initiation of new anticancer therapy, whichever occurs first.
- x. Only participants in the combination therapy arm need to undergo pulmonary function tests at screening and at Weeks 12 and 24 of study treatment.

Table 19 Study Interruption: Schedule of Assessments – Dose Expansion Monotherapy and Combination Therapy Cohort

	Alternate Approach(es)	Treatment ^a																Pembrolizumab Monotherapy	EOT ^s
		Cycle 1						Cycle 2						Cycles 3 to 4 ^b		Cycles 5 to 6 ^c		Doses 5 to 17 ^d	
Visit Days		1	2	4	8	15	22	1	2	4	8	15	22	1	15	1	15	Every 6 weeks	
Window(days)		0	0	± 1	± 1	± 1	± 1	0	± 1	± 1	± 1	± 1	± 1	± 3	± 1	± 3	± 1	± 3	+ 7
Physical Examination ^e	Except for ASP0739 and/or Pembrolizumab administration days at study site, may be obtained at local facility and results submitted to PI	X ^e	X	X ^z	X	X	X	X ^e	X	X ^z	X	X	X	X ^e	X	X ^e	X	X ^e	
Vital Signs ^f	Except for ASP0739 and/or Pembrolizumab administration days at study site, may be obtained at local facility and results submitted to PI	X	X	X ^z	X	X	X	X	X	X ^z	X	X	X	X	X	X	X ^f	X	
ECOG Performance	Except for ASP0739 and/or Pembrolizumab administration days at study site, may be obtained remotely via telemedicine visit or at local facility and results submitted to PI	X ^g	X		X	X	X	X ^g	X		X	X ^h	X	X ^{g,h}	X ^h	X ^{g,h}	X ^h	X ^{g,h}	

Table continued on next page

	Alternate Approach(es)	Treatment ^a														Pembrolizumab Monotherapy	EOT ^s		
		Cycle 1						Cycle 2						Cycles 3 to 4 ^b		Cycles 5 to 6 ^c		Doses 5 to 17 ^d	
Visit Days		1	2	4	8	15	22	1	2	4	8	15	22	1	15	1	15	Every 6 weeks	
Window(days)		0	0	± 1	± 1	± 1	± 1	± 1	0	± 1	± 1	± 1	± 1	± 3	± 1	± 3	± 1	± 3	+ 7

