- b. After the first 2 cycles, participants who have not met any individual treatment discontinuation criteria and are receiving clinical benefit (defined as radiological response or SD, or reduction of disease-related symptoms) will continue further treatment of ASP0739 as decided by the investigator.
- c. After the first 4 cycles, participants who achieve PR or SD may continue further treatment of ASP0739 in cycles 5 and 6. Participants who reach CR will not receive additional doses of ASP0739.
- d. Participants in combination therapy only will continue to receive pembrolizumab as monotherapy for doses 5 up to 17. If participant receives at least one dose of ASP0739 but discontinues combination treatment of ASP0739 at any time prior to C5D15, then the participant may continue pembrolizumab as monotherapy for up to 96 weeks for a total of 17 doses of pembrolizumab total for the study.
- e. Height measurement performed at screening only. If height cannot be measured at the screening visit, it can be collected at any time during the course of the study, but should be recorded for the screening visit. Weight measurement performed at screening and day 1 of each cycle.
- f. The following vital sign assessments schedules apply:
 - At C1D1 and any visit when pembrolizumab and ASP0739 are administered together, vital signs are obtained predose (-1 hour from start of pembrolizumab infusion), within 15 min prior to start of the pembrolizumab infusion, 15 min (-5 to +10 min window) after the start of pembrolizumab infusion, at the end of pembrolizumab infusion (-5 to +10 min window), 30 min (\pm 10 min) after completion of the pembrolizumab infusion, within 15 min prior to start of ASP0739 infusion, every 15 min (-5 to +10 min window) during ASP0739 infusion, at the end of ASP0739 infusion (-5 to +10 min window), and post dose (+30 min, +1, +2, +3 and +4 hours [\pm 10 min window each] from end of ASP0739 infusion).
 - ASP0739 dosing only: vital signs will be obtained within 15 min prior to start of ASP0739 infusion, every 15 min (-5 to +10 min window) during ASP0739 infusion, at the end of ASP0739 infusion (-5 to +10 min window) and 30 min (\pm 10 min) after completion of the ASP0739 infusion. If participants are still available, additional optional vital sign assessments 3 hours (\pm 10 min) and 4 hours (\pm 10 min) after completion of the ASP0739 infusion will be obtained.

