 - Pembrolizumab dosing only: vital signs will be obtained within 15 min prior to start of the pembrolizumab infusion, -15 min (-5 to +10 min window) after the start of pembrolizumab infusion; at the end of pembrolizumab infusion (-5 to +10 min window), as well as, at 30 min (\pm 5 min), 1 hour (\pm 10 min) and 2 hours (\pm 10 min) after completion of the pembrolizumab infusion for participants in the combination therapy.
- g. Obtain predose.
- h. Obtain predose if participant receives pembrolizumab at the same visit.
- i. 12-lead ECGs will be recorded in triplicate (at least 2 min apart per time point) and read locally. On IP administration days, ECG will be obtained:
 - At C1D1 and any visit when pembrolizumab and ASP0739 are administered together: ECGs are obtained predose (-1 h from start of pembrolizumab infusion) and 1 to 2 h post dose of ASP0739.
 - ASP0739 dosing only: ECGs are obtained predose (-1 h from start of ASP0739 infusion) and 1 to 2 h post dose of ASP0739.
 - Pembrolizumab dosing only: ECGs are obtained predose (-1 h from start of pembrolizumab infusion) and 1 to 2 h post dose of pembrolizumab.

Footnotes continued on next page

- j. Urine or serum pregnancy test will be performed in women of childbearing potential. On treatment visit days, test must occur prior to IP administration.
- k. Laboratory tests will be analyzed by the institution's local laboratory. However, sample results must also be submitted for centralized data entry. Laboratory test may be repeated during the screening period. For participants in combination therapy arm, troponin levels will be obtained at screening; thereafter, weekly for 6 weeks and subsequently every second week for 6 weeks.
- l. Thyroid panel including triiodothyronine or free triiodothyronine, free thyroxine and thyroid stimulating hormone will be measured prior to receiving pembrolizumab for participants in the combination cohort (Screening, C2D15 then every 6 weeks).
- m. Whole blood for optional PGx study may be collected at C1D1 prior to IP administration.
- n. See [Table 5](#) for collection schedule for ASP0739 single agent and ASP0739 and pembrolizumab combination therapy.
- o. Archival tumor specimen at a minimum of 1 FFPE tumor tissue block with adequate viable tumor cells (preferred) OR a minimum of 20 FFPE unstained serial slides are required.

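### An uninterrupted ASP0739 infusion lasts 8.3 to 12.5 min, so the 15-minute vital-sign rule requires no reading during it; Table 19 also transposes the post-infusion readings

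*Protocol*

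**What the plan says.** Protocol Section 6.1.1 has ASP0739 diluted "to approximately 50 mL and administered by intravenous infusion at 4 to 6 mL/min infusion rate". It states no infusion duration.

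The timing of vital signs on dosing days is set in Table 1 footnote g, Table 2 footnote f, Table 18 footnote g and Table 19 footnote f. All four use the same wording for readings during and at the end of the infusion: "every 15 min (-5 to +10 min window) during ASP0739 infusion, at the end of ASP0739 infusion (-5 to +10 min window", with one further reading in the 15 min before the start. Section 7.2.2 only refers back to the schedules and adds no reading of its own.

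For the period after the infusion, the footnotes differ:

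- Table 2 footnote f, ASP0739 alone: "at the end of ASP0739 infusion (-5 to +10 min window), as well as, 30 min" (±5 min), then 1 h and 2 h. Tables 1 and 18 agree.
- Table 19 footnote f, ASP0739 alone: "at the end of ASP0739 infusion (-5 to +10 min window) and 30 min" (±10 min), then straight to the optional 3 h and 4 h readings.
- Table 19 footnote f, pembrolizumab alone: "at the end of pembrolizumab infusion (-5 to +10 min window), as well as, at 30 min" (±5 min), then 1 h and 2 h.

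Table 19 is the crisis version of Table 2. Its vital-signs row reads "Except for ASP0739 and/or Pembrolizumab administration days at study site, may be obtained at local facility and results submitted to PI". The introduction to the alternative schedules adds: "No alternative measures are permissible for C1D1 and ASP0739 and/or pembrolizumab dosing days during combination therapy".

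**The concern.** A rule that speaks of readings during the infusion suggests that the authors wanted at least one. For an infusion shorter than the interval, the rule produces none.

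The point matters because infusion-related reactions are an adverse event of special interest in SAP Section 5.2.3, and Protocol Section 2.3.1.1 lists changes in heart rate and blood pressure among their signs. Some responses are possible only while the infusion is running: Table 14 calls for stopping it from grade 2 onwards. In the combination safety lead-in, a reaction that forces the infusion to be discontinued is a dose-limiting toxicity (Section 4.1).

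The Table 19 discrepancy looks like text placed in the wrong bullet, because the 30-minute windows have moved along with the readings. A site following that footnote would measure less after the first-in-human product and more after pembrolizumab.

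**Working it through.** The plan gives no ASP0739 infusion time, so there is no figure to reproduce. The inputs are the volume and rate in Section 6.1.1 and the windows in the four footnotes.

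**1. Duration = volume / rate**
- 50 / 6 = 8.3 min; 50 / 5 = 10 min; 50 / 4 = 12.5 min.
- The volume is approximate. Assuming 10% either way, 45 mL takes 7.5 to 11.25 min and 55 mL takes 9.2 to 13.75 min. Reaching 15 min needs 60 mL at 4 mL/min, or 50 mL at 3.33 mL/min or slower.

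**2. Does any window force a reading during the infusion?**
- The 15-minute reading may be taken from 15 - 5 = 10 min to 15 + 10 = 25 min after the start. It overlaps the infusion only if 50 / r > 10, that is r < 5 mL/min. At 4 mL/min the overlap is 12.5 - 10 = 2.5 of its 15 min; at 5 to 6 mL/min there is none.
- The end-of-infusion window opens 5 min before the end, but 10 of its 15 min lie after the end.
- Required readings while the infusion runs: 0.

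**3. The same check for pembrolizumab**
- Its infusion takes 30 min (-5/+10), so 25 to 40 min. Its reading at 15 min (-5/+10) falls between 10 and 25 min, which is never later than the end of the shortest permitted infusion.

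**4. Longest permitted gap around an ASP0739 infusion**
- Earliest reading before the start plus duration plus latest end reading: 15 + 8.3 + 10 = 33.3 min at 6 mL/min, and 15 + 12.5 + 10 = 37.5 min at 4 mL/min.
- Up to 15 min of each precedes dosing, which leaves 18.3 to 22.5 min after the infusion starts.
- The nominal spacing from start to end is 8.3 to 12.5 min.

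**5. Prolonged infusions**
- Assuming the whole 50 mL is run at half rate (2 to 3 mL/min), as after a grade 2 reaction in Table 14, the infusion takes 16.7 to 25 min. The 15-minute rule then applies.

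**6. Post-infusion readings, side by side**

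| Footnote | ASP0739 alone | Pembrolizumab alone |
|---|---|---|
| Tables 1, 2 and 18 | 30 min (±5), 1 h, 2 h | 30 min (±10) |
| Table 19 | 30 min (±10) | 30 min (±5), 1 h, 2 h |

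Required readings go from 3 to 1 after ASP0739 alone and from 1 to 3 after pembrolizumab alone. The optional 3 h and 4 h readings stay with ASP0739, and the bullet for combined dosing is unaffected.

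**The case against.** **The clock might not start with the infusion.** The footnotes do not say so. If the 15 min runs from the reading before the infusion, taken s minutes before the start, the next reading is nominally due at 15 - s. With s = 10 that is 5 min into the infusion, and the longest gap becomes 15 + 10 = 25 min. This is a fair caveat, but it does not rescue the rule. With s = 10 the window still runs to 25 - 10 = 15 min, past the end at every permitted rate, and with s near 0 the reading is nominally due at 15 min. At 6 mL/min the window would close before the infusion ends only if s exceeded 25 - 8.3 = 16.7 min, which is not allowed.

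**The rule may be redundant rather than broken.** Nominal readings bracket a short infusion more closely than 15 min, and nothing in the documents explicitly demands a mid-infusion reading of a 10-minute infusion. This stands in part: the gap of 33.3 to 37.5 min is a worst case. The pembrolizumab footnote nevertheless secures a reading during the infusion.

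**Other safeguards exist.** Table 14 asks for a physician at hand and resuscitation equipment at the bedside. Section 4.1 requires at least 4 h of observation after the first dose in dose escalation and a 7-day hospital stay in the Japanese lead-in. No infusion reactions were seen nonclinically, and the first 4 participants raised no safety concern (Section 2.3.1.1). All of this stands and limits the risk, but none of it sets a timed vital-sign measurement during the infusion.

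**Table 19 may not govern dosing days.** Section 10.12 keeps Tables 1 to 4 as the expected schedule unless alternatives are discussed with the medical monitor, and the vital-signs row exempts administration days. This also stands. The footnote therefore contradicts Table 2 rather than clearly overriding it.

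**Conclusion.** Both parts hold, with limits.

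For an uninterrupted infusion at the stated volume and rate, with the interval counted from infusion start (the natural reading), the footnotes require no vital-sign reading during the infusion, at any of up to 6 infusions per participant. A 10% departure from 50 mL does not change this.

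Table 19 footnote f transposes the two sets of post-infusion readings. The effect is confined to expansion participants on the crisis schedule. The SAP (Section 1) reports early termination and no combination treatment, which limits the practical exposure further. No endpoint or planned analysis is affected.

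A reader might infer three stronger things that the documents do not support:

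- That participants go unmeasured during the infusion. A reading is permitted through the end-of-infusion window and, below 5 mL/min, through the 15-minute window.
- That they may go more than half an hour on drug without a reading. That gap needs every window at its limit and includes up to 15 min before dosing.
- That Table 19 removes the 1 h and 2 h readings after ASP0739 alone. They are lost only if a site follows that footnote over Table 2.

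**What to change.** 1. In the vital-sign footnotes of Tables 1, 2, 18 and 19, require one reading 5 min (±2 min) after the ASP0739 infusion starts. The latest time is 7 min, before the shortest infusion ends at 8.3 min; the upper side of the window must stay below 8.3 - 5 = 3.3 min.
2. Keep the 15-minute rule for infusions that are prolonged or restarted at half rate.
3. Preferably narrow the end-of-infusion window to 0 to +5 min.
4. In Table 19 footnote f, restore the Table 2 footnote f wording for both single-product bullets.

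With items 1 and 3, the longest permitted gap before the new reading is 15 + 7 = 22 min and after it 12.5 + 5 - 3 = 14.5 min. The new reading alone brings the maximum to 22 min; the narrower end window shortens only the second interval, from 12.5 + 10 - 3 = 19.5 min. At 6 mL/min a reading at 7 min comes just 1.3 min before the end of the infusion, so the two readings can nearly coincide.

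The cost is one more vital-sign reading per infusion (up to 6 per participant), by staff already present, and edits to four footnotes. The Table 19 correction adds nothing beyond the Table 2 schedule.
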